**Methodology**  
*Details of the Intervention*

Women will be randomized to one of the two vaginal estrogen arms or placebo in a 1:1:2 fashion. For those randomized to the ring, the ring will be placed by the provider in 3 month intervals at their visits. Subjects randomized to cream arm will receive 0.5g (0.312 mg) conjugated estrogen vaginal cream per vagina at bedtime two times per week. The placebo cream will be administered in a similar fashion. These cream tubes will be weighed at baseline and again at the every 3 month office visits to assess adherence. They will also be given diaries to keep track of their medication administration. Subjects will be called once a month for the first 3 months by study personnel to assess for adverse events as well as UTI symptoms. After the first 3 months, a relationship will be established with study personnel and the participants will be encouraged to call with symptoms.

Written quality of life questionnaires will be administered at baseline, at the end of randomization or 6 months and at drop out (if possible) or 12 months. The questionnaires include the OAB-SAT-q, MESA, UDI-6, FSFI and PSQ, GPI and EPI rating scales and are previously validated questionnaires referenced above in *Overall Design* [26-31]. These will assess global QOL, as well as irritative bladder symptoms and sexual function. We will also collect baseline data with respect to medical history and concomitant pelvic medicine diagnoses.

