#### *UTI definitions*

There is debate over the optimal definition for recurrent UTI. In general, the most commonly accepted definition is the presence of 3 or more symptomatic UTI in 1 year or 2 in 6 months [16]. Symptomatic UTI has been defined by the Center for Disease Control (CDC) as a combination of signs, symptoms and laboratory measures. We will use this definition of UTI for our primary outcome: individuals experiencing at least one symptom (fever >38 degrees C, urgency, frequency, dysuria OR suprapubic tenderness) AND a positive urine culture that is  $\geq 10^5$  microorganisms per milliliter (mL) of urine with no more than 2 species of microorganisms. Alternatively, if the specimen is collected via catheterization, a culture as low as  $10^3$  microorganisms per mL of urine will be considered positive. Given that guidelines do not require primary care physicians to obtain urine cultures to diagnose a urinary tract infection, we will only require one positive urine culture and the other urinary tract infections may be diagnosed with urinalysis. From a practical and clinical standpoint, UTIs are generally diagnosed based on symptoms, urine analysis and/or culture and rarely are catheterized specimens collected in routine practice. Thus, presence of UTI will be determined using symptoms and a positive clean-catch culture as the primary outcome unless a patient cannot obtain a clean catch (in which case we will use a catheterized specimen). In order to minimize false positives, urine will be placed in preservative within 10 min of collection. Urine cultures are up to 95% sensitive and 99% specific at diagnosing UTI [17].

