The primary outcome is occurrence of one or more symptomatic UTIs within 6 months of treatment. Subjects will perform a clean catch for a urine culture when they have symptoms of a UTI using the CDC definition of symptoms, as above. If the subject cannot perform a clean catch themselves, a provider may obtain a catheterized specimen as clinically indicated, in which case the threshold for bacterial count will decrease to  $10^3$  microorganisms per mL. Secondary outcomes include assessing rate of UTI over the course of the year in those women who received placebo and then vaginal estrogen, as well as comparing the rates of UTI in the placebo and vaginal estrogen group. Quality of life (QOL) questionnaires will be administered at baseline, at the end of randomization and at drop out or 12 months. There are no validated questionnaires that assess UTI specifically, therefore we have chosen questionnaires which relate to general QOL, as well as those which include symptoms similar to that of UTI. In addition, we know that vaginal estrogen can treat dyspareunia, so we will capture sexual function. We will be using the SF 12, as well as the overactive bladder satisfaction questionnaire (OAB-SAT-q), the medical, epidemiological and social aspects of aging questionnaire (MESA), the urogenital distress inventory (UDI-6) and the female sexual function index (FSFI) along with the patient satisfaction global ratings: patient satisfaction question (PSQ), estimated percent improvement (EPI) and global perception of improvement (GPI). The SF 12 is a general quality of life questionnaire initially used to survey health status [26]. The OAB-SAT-q is a questionnaire evaluating satisfaction pertaining to overactive bladder symptom treatment, symptoms which are similar to those of a UTI [27]. The MESA questionnaire explores lower urinary tract symptoms [28]. The UDI-6 is the short form of the urogenital distress inventory which surveys life impact and symptom distress of urinary incontinence and related issues in women [29]. The FSFI is a validated questionnaire assessing female sexual function [30]. The PSQ, EPI and GPI are patient global ratings, satisfaction, perception of improvement and estimated percent improvement validated previously in the treatment of urinary incontinence [31]. These questionnaires will allow us to assess whether general quality of life, irritative urinary symptoms, as well as sexual function are improved by vaginal estrogen, which could occur secondary to the correction of atrophic vaginitis alone. We will also assess whether QOL changes when UTIs occur with less frequency and will assess overall patient satisfaction with treatment. We will also be evaluating adherence in each treatment arm. Adherence with creams will be assessed by medication diary and weighing the tubes at each 3 month visit and vaginal rings will be accounted for by confirming that the ring is still in place in the vagina and then exchanging it for the new ring. Adherence is defined as  $\geq 80\%$  usage.

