### ***Outcomes***

The primary outcome will be the occurrence of symptomatic UTI within the 6 month treatment period. Clean catch urine culture will be collected whenever subjects report symptoms of a UTI: fever (>38 degrees C), urgency, frequency, dysuria or suprapubic tenderness. Standing orders for urine analysis and culture will be present at the local institution's lab and women will be asked to have all urine labs done at the parent site as per standard clinical practice. If subjects are not able to submit a specimen to the local site, lab orders will be faxed to a local laboratory for collection and results sent to parent institution as per clinical care standards. Treatment will be up to the discretion of the treating physician. If they are unable to perform a clean catch, they may come in to the office for a catheterized specimen according to the treating physician's clinical recommendations. As these cultures would be obtained regardless of study participation, they will be obtained and billed according to standard of care. The presence of a UTI in the 6 month window will be the primary outcome of the study, but secondarily we will assess the rate of UTIs over the course of the year that occur in order to assess efficacy.

Other secondary outcomes include QOL questionnaires mentioned above. These will help us to look at changes in general QOL, as well as irritative bladder symptoms and sexual function, impacted by study drug. Adherence will also be assessed. We will weigh tubes of cream to determine adherence with creams, as well as collect medication diaries (adherence will be defined as  $\geq 80\%$  use as measured by weight of the vaginal cream tubes). For the ring, compliance will be assessed based on presence of the ring vaginally at 3 month visits.

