### ***Analysis***

#### ***Sample Size Consideration***

The primary outcome is whether there is any occurrence of symptomatic UTI at the end of the randomized

treatment period. Based on the literature [15] we assume that the rate of at least one UTI in the placebo group is 63%. With 20 subjects at the end of the randomized treatment period in each of the two treatment groups, we will have 80% power to detect a difference using Fisher's exact test if the corresponding rate in an active treatment group is 16% [15] under a two-sided significance level of 0.05. A total sample size of 48 (24 subjects per group) will be needed allowing for 20% attrition seen to date in the study.

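### Staff ask about UTI symptoms monthly only in months 1–3 of a 6-month primary window, so UTIs in months 4–6 may be missed; uniform enquiry to month 6 is a cheap safeguard

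*Combined protocol and SAP*

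**What the plan says.** All references are to the combined protocol and SAP.

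- **Window.** Section 9, Overall Design: "The primary outcome is occurrence of one or more symptomatic UTIs within 6 months of treatment". The Outcomes subsection repeats the 6-month window.
- **How symptoms come to light.** Section 9, Methodology, has staff telephone each woman monthly for 3 months to ask about adverse events and UTI symptoms. Then: "After the first 3 months, a relationship will be established with study personnel and the participants will be encouraged to call with symptoms".
- **How an event is confirmed.** Section 9, Outcomes: "Clean catch urine culture will be collected whenever subjects report symptoms of a UTI". Section 7, UTI definitions, requires at least one symptom and a positive culture for the primary outcome.
- **Treatment elsewhere.** The same subsection of section 7 has a sentence that begins "Given that guidelines do not require primary care physicians to obtain urine cultures to diagnose a urinary tract infection". It goes on to require only one positive culture and to let the other UTIs be diagnosed by urinalysis. The inclusion criteria in section 10 state that same rule for past UTIs.
- **Visits.** Those at months 3 and 6 list cream weighing, the ring check and exchange and, at month 6, questionnaires. No UTI history is listed.

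**The concern.** A symptom that nobody reports leads to no culture, and without a culture there is no event. For 3 months staff prompt the report; for the next 3 the woman must initiate it. The method of ascertainment therefore changes halfway through the primary window, and the only reason given is that a relationship with staff will have formed.

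Three things are at stake.

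1. If UTIs in months 4–6 are missed equally in both arms, both observed rates fall, the risk difference shrinks and power drops. The design has little to spare.
2. Secondary objective 1b compares UTI rates in women who start on placebo and then switch to estrogen. The first period has 3 months of prompted reporting and the second has none, so part of any apparent fall could come from ascertainment.
3. A UTI treated elsewhere without a culture apparently would not count under section 7. This can happen in either half of the window.

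**Working it through.** **Inputs from the plan** (section 9, Sample Size Consideration): placebo rate 63%, active rate 16%, 20 evaluable women per group, power stated as that "to detect a difference using Fisher's exact test" and "under a two-sided significance level of 0.05". Allocation of 1:1:2 makes pooled estrogen v placebo 1:1.

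**Step 1: the plan's own figure.** Summing the two binomial distributions over all tables with two-sided Fisher p ≤ 0.05 gives 82.3% power at 20 v 20. The continuity-corrected formula gives 20 per group. The stated 80% is reproduced, with a margin of 2.3 points.

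**Step 2: model for missed events.** The documents give no capture rate, so the following are assumptions: constant hazard in each arm, full capture in months 1–3, and a fraction c of UTIs captured in months 4–6, equal in both arms.

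- Monthly hazard λ = −ln(1 − p)/6. Placebo: −ln(0.37)/6 = 0.1657. Active: −ln(0.84)/6 = 0.0291.
- Probability of at least one captured UTI = 1 − exp[−λ(3 + 3c)].
- Example, c = 0.8: 3 + 2.4 = 5.4 effective months. Placebo 1 − exp(−0.1657 × 5.4) = 59.1%; active 1 − exp(−0.0291 × 5.4) = 14.5%.

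| Capture in months 4–6 | Placebo | Active | Difference (points) | Power, 20 v 20 |
|---|---|---|---|---|
| 100% | 63.0% | 16.0% | 47.0 | 82.3% |
| 90% | 61.1% | 15.3% | 45.8 | 81.0% |
| 80% | 59.1% | 14.5% | 44.6 | 79.4% |
| 60% | 54.9% | 13.0% | 41.8 | 75.2% |
| 50% | 52.6% | 12.3% | 40.3 | 72.6% |

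Power crosses 80% at c of about 84%. The risk ratio hardly moves (16.0/63.0 = 0.25; 12.3/52.6 = 0.23).

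**Step 3: a harsher model.** In Step 2 a woman whose first late UTI is missed can still be captured at a second. If instead a fraction m of women whose first UTI falls in months 4–6 is scored event-free, power is 80.2% at m = 10%, 77.8% at 20% and 69.5% at 50%, and crosses 80% near m = 11%.

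**Step 4: unequal loss.** Under Step 2, if 80% capture applied to placebo only, the rates would be 59.1% v 16% and power 75.3%. With equal loss and no treatment effect, the size of the test stays below 0.05 (about 0.022 to 0.025).

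**Step 5: objective 1b.** Suppose estrogen has no effect and the months 4–6 capture rate persists to month 12. The recorded rate in months 7–12 relative to months 1–6 is then 6c/(3 + 3c). At c = 0.8 this is 4.8/5.4 = 0.89, an apparent fall of 11%. At c = 0.5 it is 3/4.5 = 0.67, an apparent fall of 33%.

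**The case against.** The case for leaving the plan alone has weight.

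- **No missed-event rate is given.** A reader might infer that second-half events are under-counted and that power is in fact below 80%. The documents do not support that: at 90% or 85% capture, power is still 81.0% or 80.2%. This point stands.
- **The 63% may already be an observed rate.** The sample-size section takes it from a cited trial and does not say that it assumes full capture. If that trial also relied on symptom reports, thinning the figure again overstates the loss. This also stands.
- **No rule scores uncultured UTIs as no event.** A reader might take that as written. It is only inferred from the section 7 definition, and the urinalysis sentence there could be read as an outcome rule instead of an eligibility rule. The fault is ambiguity. Nor does this loss begin at month 3: it can occur at any time, and a call cannot recover a culture after treatment. The table above does not measure it.
- **Safeguards exist.** There are standing orders, orders faxed to outside laboratories with results returned, visits every 3 months with higher payment at months 3 and 6, a quarterly data review that includes UTI counts, and an authorization to collect UTI and clinic-visit data. These reduce the risk but do not remove it. The orders help only once a woman reports, the review checks data already held, and no listed procedure uses the visits or the authorization to ask about missed episodes.
- **Enrolment is complete** (section 8), so extra calls can reach only women not yet past month 6. This limits the remedy to that extent.

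**Conclusion.** Prompted symptom enquiry stops halfway through the primary window, and nothing listed replaces it. Second-half UTIs may therefore be missed. This is a weakness in ascertainment, not an error in the stated power, which reproduces.

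The likely cost is modest and conditional: about 1 point of power at 90% capture, 3 at 80%, 7 at 60% and 10 at 50%, given constant hazard, full capture in months 1–3 and equal loss. It is smaller if the 63% already reflects symptom-driven reporting, and larger if women rather than episodes are lost or if the loss falls mainly on placebo. For objective 1b the consequence is possible bias toward an apparent benefit. Scoring of uncultured UTIs treated elsewhere is unclear in both halves of the window and needs a written rule. The point merits action because the remedy is cheap.

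**What to change.** 1. Continue the same monthly symptom call through month 6 for women still in the randomized period.
2. At the existing month 3 and month 6 visits, ask every woman in both arms the same question about UTIs treated elsewhere, and request the results under the authorization described in section 16. For women already past month 6, make this record check retrospectively.
3. Keep the culture-based primary outcome. State whether the urinalysis sentence in section 7 applies to eligibility only, and how a UTI treated without a culture is scored.
4. Add a supporting analysis that counts symptomatic UTIs treated without a culture as events.
5. When reporting objective 1b, state that prompted calls were made in only part of the follow-up.

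**Cost.** At most 3 short calls per woman still in months 4–6, by staff who already make such calls. The ceiling is 3 × 48 = 144, which would apply only if no woman had yet passed month 3. Add one question at existing visits, some record requests and one extra analysis. No treatment or visit changes.

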### ***Safety and Toxicity Measures***

If subjects in any arm develop 3 UTIs in the 6 month treatment period, they will be unblinded. If on placebo, they will be provided active study drug as would have been done at the 6 month visit or if they are on study drug, they will be treated according to the provider's clinical practice and their outcomes recorded for the remainder of the study. Six month outcome assessments will be administered early to capture QOL data for the secondary analyses. We will also be monitoring for adverse events monthly with phone calls for the first 3 months, specifically querying symptoms of pain, bleeding or abnormal discharge which would prompt evaluation for relatedness to study participation. Events related to participation will not be billed to insurance, however, any events which are part of routine clinical care (ie. UTI or other pelvic floor disorder treatment such as urinary incontinence) will be billed according to standard clinical care. After that subjects will be encouraged to call with any adverse reactions. Attribution of these events to study participation will be assigned by the investigator and reported to the IRB according to local policy.

### ***Outcomes***

The primary outcome will be the occurrence of symptomatic UTI within the 6 month treatment period. Clean catch urine culture will be collected whenever subjects report symptoms of a UTI: fever (>38 degrees C), urgency, frequency, dysuria or suprapubic tenderness. Standing orders for urine analysis and culture will be present at the local institution's lab and women will be asked to have all urine labs done at the parent site as per standard clinical practice. If subjects are not able to submit a specimen to the local site, lab orders will be faxed to a local laboratory for collection and results sent to parent institution as per clinical care standards. Treatment will be up to the discretion of the treating physician. If they are unable to perform a clean catch, they may come in to the office for a catheterized specimen according to the treating physician's clinical recommendations. As these cultures would be obtained regardless of study participation, they will be obtained and billed according to standard of care. The presence of a UTI in the 6 month window will be the primary outcome of the study, but secondarily we will assess the rate of UTIs over the course of the year that occur in order to assess efficacy.

Other secondary outcomes include QOL questionnaires mentioned above. These will help us to look at changes in general QOL, as well as irritative bladder symptoms and sexual function, impacted by study drug. Adherence will also be assessed. We will weigh tubes of cream to determine adherence with creams, as well as collect medication diaries (adherence will be defined as  $\geq 80\%$  use as measured by weight of the vaginal cream tubes). For the ring, compliance will be assessed based on presence of the ring vaginally at 3 month visits.

### ***Analysis***

#### ***Sample Size Consideration***

The primary outcome is whether there is any occurrence of symptomatic UTI at the end of the randomized

treatment period. Based on the literature [15] we assume that the rate of at least one UTI in the placebo group is 63%. With 20 subjects at the end of the randomized treatment period in each of the two treatment groups, we will have 80% power to detect a difference using Fisher's exact test if the corresponding rate in an active treatment group is 16% [15] under a two-sided significance level of 0.05. A total sample size of 48 (24 subjects per group) will be needed allowing for 20% attrition seen to date in the study.

#### *Data Analysis*

Subject characteristics including baseline measures will be compared across the randomized groups using t-test or chi-squared test (or their nonparametric / small sample counterparts) as appropriate, and will be adjusted in a regression model in addition to the primary comparisons above. It is known that even if the characteristics are balanced across the groups, such adjust can improve the efficiency of the comparisons [32]. For the secondary outcomes, frequencies (counts) of UTIs in the randomized period as well as the additional follow-up period will be compared between groups using a Poisson model; the QOL outcomes will be compared between groups using t-tests, and between baseline and 12 months within an active treatment group using paired t-test; adherence will be compared between the ring group and the active cream group as a dichotomous variable, with adherence for the latter group defined as  $\geq 80\%$ . While the primary comparisons are intent-to-treat, secondary comparisons will be carried out among those subjects who have adhered. In addition, for the variables that are collected at three or more time points, longitudinal data analysis will be performed using random effects models. As the attrition rate is expected to be as high as 20%, whether the missing data mechanism might be informative will be checking using methods such as those described by Ridout et al. [33] in case of informative (non-ignorable) missingness, sensitivity analysis will be carried out.

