
The open label portion of the study will start at month 6. All of those women using placebo cream will be allowed to choose a vaginal estrogen preparation to use for the remainder of the study (ring or cream). Those women initially randomized to vaginal estrogen will be allowed to choose which vaginal estrogen preparation they want to continue with. The rationale behind an open label portion of the study is an incentive to participate. Vaginal estrogen is available to patients via prescription, as an off label indication, but coverage for this therapy can be limited and treatment costly (up to \$300 per prescription refill). The open label portion of the study should provide incentive for women to enroll when the study drug is already available, as will modest reimbursement for study visits. We will also be able to compare the rates of UTI in those women who received placebo initially to their rate of UTI on drug.

Eligible women will be consented and block randomized using preset, opaque and sealed envelopes. These cards will either say “study drug 1, 2 or 3” and will be placed in numbered envelopes in a random order and selected by study staff and dispensed to the subject. These drugs will be stored in a locked cabinet in the Female Pelvic Medicine clinic. After the subject receives her study drug, she will receive administration instructions. If the assigned treatment is a ring, the subject will have it placed by the provider, if it is a cream, the cream will be weighed at baseline and she will be shown how to place it vaginally herself and instructed on bringing the remaining study drug to each 3 month visit for weighing.

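### The 6-month quality-of-life comparison is planned as a t-test that ignores the baseline score, and no baseline-adjusted month-6 contrast is named as the main test

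*Combined protocol and SAP*

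**What the plan says.** Secondary hypothesis 2a (Specific Aims) is a between-group claim: better QOL on vaginal estrogen than on placebo at 6 months. The baseline data exist. Overall Design states "Quality of life (QOL) questionnaires will be administered at baseline, at the end of randomization and at drop out or 12 months", and Methodology repeats this: "Written quality of life questionnaires will be administered at baseline, at the end of randomization or 6 months".

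The Data Analysis section contains three sentences that bear on how hypothesis 2a is tested:

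- The method assigned to QOL: "the QOL outcomes will be compared between groups using t-tests, and between baseline and 12 months within an active treatment group using paired t-test".
- Baseline characteristics and measures "will be adjusted in a regression model in addition to the primary comparisons above", with the reason that "such adjust can improve the efficiency of the comparisons". The text then moves to the secondary outcomes and gives each its own method.
- A further analysis: "for the variables that are collected at three or more time points, longitudinal data analysis will be performed using random effects models". QOL has three scheduled assessments, so it qualifies.

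The Outcomes section says of the questionnaires: "These will help us to look at changes in general QOL". That hints at change scores, but the analysis text does not confirm it.

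**The concern.** A reader cannot tell from the plan which analysis tests hypothesis 2a. The t-test could be run on 6-month scores or on changes. Which is more precise depends on a correlation that nobody has stated: change is the noisier choice when it is below 0.5 and the better one when it is above. Neither makes the best use of a baseline score that is already collected.

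The two neighbouring sentences do not close the gap. The adjustment sentence refers to the primary comparisons. The random effects models are introduced as an addition, with no fixed effects, no stated handling of baseline and no month-6 contrast. Their last time point also falls after the switch: "All of those women using placebo cream will be allowed to choose a vaginal estrogen preparation to use for the remainder of the study". Safety and Toxicity Measures moves placebo women to active drug earlier still, after a third UTI. An overall group effect or a 12-month slope would therefore mix randomized and open-label periods and would not test hypothesis 2a.

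Two things are at stake. One is precision, in a trial that stops enrolling at 40 completers. The other is an open choice among score, change, adjusted and longitudinal results across several questionnaires.

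**Working it through.** **Inputs from the documents.** Sample Size Consideration gives 20 evaluable women per group, two-sided 0.05 and 80% power; Human Subjects gives 40 completers in total. The 1:1:2 ring, cream and placebo allocation makes pooled estrogen versus placebo 1:1. All of these were set for UTI occurrence; the plan states no power, SD or effect size for QOL. The sample size itself reproduces: exact power of Fisher's test for 63% versus 16% with 20 per group is 82.3%, against the stated 80%.

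**Assumptions.** The correlation ρ between baseline and 6-month scores is not given, so 0.3, 0.5 and 0.7 are used. The SD is taken as equal at both times, and differences are in SD units.

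**Variance of the group difference, relative to a t-test on 6-month scores (= 1)**

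- t-test on change: 2(1 − ρ) = 1.40, 1.00, 0.60.
- ANCOVA, large sample: 1 − ρ² = 0.91, 0.75, 0.51.
- ANCOVA against change: (1 − ρ²) / [2(1 − ρ)] = (1 + ρ)/2 = 0.65, 0.75, 0.85.

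In large samples ANCOVA therefore cuts the variance by 9%, 25% and 49% against scores, and by 35%, 25% and 15% against change. As equivalent extra women (1/ratio − 1), that is 10%, 33% and 96% against scores, and 54%, 33% and 18% against change.

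**Cost of estimating the slope.** With n = 20 per group the ANCOVA variance is inflated by (2n − 3)/(2n − 4) = 37/36 = 1.028. The cuts shrink to 6%, 23% and 48% against scores, and to 33%, 23% and 13% against change. A simulation of 40,000 trials gave variance ratios of 0.934, 0.769 and 0.530 (scores) and 0.665, 0.766 and 0.870 (change), which agrees.

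**Detectable difference and power.** The standard error is √(v × 2/20), where v is the relative variance above. Noncentral t was used with 38 df for the t-tests and 37 df for ANCOVA, including the 37/36 factor.

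| Assumed ρ | Difference at 80% power: score | change | ANCOVA | Power for 0.5 SD: score | change | ANCOVA |
|---|---|---|---|---|---|---|
| 0.3 | 0.91 SD | 1.08 SD | 0.88 SD | 34% | 26% | 36% |
| 0.5 | 0.91 SD | 0.91 SD | 0.80 SD | 34% | 34% | 42% |
| 0.7 | 0.91 SD | 0.70 SD | 0.66 SD | 34% | 51% | 57% |

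**Cost of the unspecified choice.** At ρ = 0.3, using change instead of scores costs 1.08 − 0.91 = 0.17 SD in detectable difference. At ρ = 0.7, using scores instead of change costs 0.91 − 0.70 = 0.21 SD. ANCOVA is more precise than both at each of the three values.

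**Where ANCOVA loses.** It is less precise than the score test when (1 − ρ²) × 37/36 > 1, that is ρ² < 1/37, or ρ below about 0.16. At ρ = 0.1 the ratio is 0.99 × 1.028 = 1.02. The worst case, ρ = 0, costs about 3% in variance.

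**The case against.** The strongest reply is that the plan already holds a model that uses baseline QOL: the random effects analysis covers it, so only the month-6 contrast is unwritten. That is fair, and naming that contrast is one of the two acceptable fixes. Until it is named, however, the model does not answer hypothesis 2a.

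The adjustment sentence might also be read more widely. Later in the same section, primary comparisons are equated with intent-to-treat and secondary ones with adherent women, so the phrase could cover every randomized comparison. This is possible, but the sentence refers back to comparisons already described, and the next one gives the secondary outcomes separate methods. On the wide reading there would still be two QOL analyses and no stated order.

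It can be said that the order of the text makes the t-test the main analysis. Even so, score versus change stays open.

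Several limits stand in full. The t-test is valid, so there is no bias or type I error problem. The correlation is assumed; the gain over scores is slight at 0.3 and turns into a small loss below about 0.16. The figure of 96% more women is the top of the range, before the small-sample cost. QOL remains underpowered for a 0.5 SD effect in every scenario shown. Four of the eight instruments in Overall Design rate satisfaction or improvement with treatment and have no meaningful baseline.

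**Conclusion.** The point holds, as a matter of precision and specification for a secondary outcome. The between-group QOL test has no baseline covariate, its response variable is undefined, and no baseline-adjusted month-6 contrast is named. With 20 women per group, baseline adjustment lowers the detectable difference from 0.91 SD to between 0.88 and 0.66 SD against a t-test on scores. Against a t-test on change, the fall is from 1.08 to 0.88 SD at ρ = 0.3 and from 0.70 to 0.66 SD at ρ = 0.7. These figures rest on assumed correlations of 0.3 to 0.7 and equal SDs at both times. The change should be made because it costs little and follows the plan's own argument for adjustment. It applies to SF-12, UDI-6, MESA and FSFI only.

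**What to change.** State in Data Analysis that, for SF-12, UDI-6, MESA and FSFI, the main test of hypothesis 2a is an ANCOVA of the 6-month score on randomized group (pooled estrogen versus placebo) and baseline score. Where the six-month assessment was taken early after a third UTI, that assessment serves as the 6-month score. Alternatively, name an explicit month-6 estrogen-placebo contrast, adjusted for baseline, from the random effects model already planned. Say that any other QOL analysis is supportive. Keep unadjusted tests for OAB-SAT-q, PSQ, EPI and GPI.

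The cost is one or two sentences and one degree of freedom per model. No new data are needed, and the primary analysis and sample size do not change. Because the Progress Report says enrollment is complete and a committee that includes the statistician reviews data quarterly, date the change and record that it was made without sight of QOL results by group. While editing, reconcile the instrument lists: SF-12 appears in Overall Design but not in the list under Methodology.
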